3.1.2 Objective

The objective is to determine specific molecular breath patterns by secondary electro ionisation-mass spectrometry (SESI-MS) during and 8 weeks after a severe exacerbation requiring hospitalization. Furthermore, molecular breath patterns will be assessed for correlation and association to clinical outcomes and treatment.

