3.2.2 Secondary Outcome Measures

Correlation of breath metabolites with symptoms (mMRC and CAT®), inflammation markers (CRP and eosinophils, exhaled NO), causative agents (sputum microbiology and viral swabs) and treatment (inhalational drugs, steroids, antibiotics).

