4.5.6 Causative agents

Sputum samples and viral smear is collected routinely during the clinical assessment during hospitalization (visit 1).

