spectrometer by Thermo Fisher. This results in sensitive and selective, yet real-time, analysis of trace vapour species.(53) Our SESI-HRMS is situated in a separate, lockable room at the University Hospital Zurich. Access to the designated room is only permitted to members of the staff. Participants will be asked to refrain from eating, drinking, chewing gum, alcohol, tobacco, caffeine use or brushing their teeth at least 1 hour before the measurements will be performed. Room temperature and lighting will be set at the same level for all measurements. Participants will exhale through a disposable mouthpiece, into a heated tube (stainless steel, Silconert coated) (50 cm long, 4 mm in diameter) connected to the curtain AUX gas port of a Orbitrap spectrometer (Thermo Fisher, Waltham, Massachusetts, USA) that is provided by DBI. The sampling tube is surrounded with an isolated heating tape at 130 °C to prevent water condensation and to minimize losses of exhaled compounds onto the walls of the tube. While performing full exhalations, the subjects will keep the volume through the sampling line at 8L/min monitored by a digital flow meter. A nano electrospray plume (FIT, Madrid, Spain), provided by DBI, will be used, where compounds of exhaled breath get ionized and subsequently are mass analysed. The technique, by which breath is analysed in real time by injecting exhaled breath into electrospray plumes of pure solvent and thus causing ionization of relevant exhaled compounds(54-56), has been referred to as secondary electrospray ionization (SESI)(57). Breathprints will be collected in real-time recording six replicates through the mouthpiece. The raw mass spectra will be exported as mzXML files for further processing using MATLAB (Mathworks, Inc). The spectra of exhaled breath will be averaged. In this process, only the last few seconds (typically around 6 sec.) of each exhalation will be considered, thus the first part of the exhalation, which reflects mostly the dead space in the upper respiratory tract, will be excluded from the analysis. SESI-MS allows for real-time breath-printing by detection of both volatile and non-volatile trace components in breath without any sample pre-treatment. The de-identified mass spectrometric breath signatures of patients are subsequently analysed by DBI with AI algorithms for spectroscopic profiling.

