4.5.8 Questionnaires

4.5.8.1 COPD Assessment Test (CAT) & modified Medical Research Council (mMRC)

For assessing symptoms, GOLD guidelines primarily recommend the use of the COPD Assessment Test (CAT) or the modified Medical Research Council (mMRC) dyspnea score. The CAT score is a patient-completed instrument to assess and quantify health-related quality of life and symptom burden in COPD patients. It comprises 8 questions, each is presented as a semantic 6-point (0-5) differential

scale, providing a total score out of 40. Scores of 0-10, 11-20, 21-30, 31-40 represent mild, moderate, severe or very severe clinical impact, respectively. The mMRC dyspnea score is a 5-point (0-4) scale based on the severity of dyspnea.(58)

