5. STATISTICS AND METHODOLOGY

5.1 Statistical analysis plan

For data processing, we will follow the same procedure as described in our previous studies [Gaugg, 2016]: raw mass spectra will be transformed to *.mzXML format using the online tool msConvert. The *.mzXML files will be imported into Matlab. Each mass spectrum is then interpolated (shape-preserving piecewise cubic interpolation method), mass calibrated using an iterative grid search algorithm, and the resulting spectra are centroided. To test the hypothesis that there is a significant difference in the values of exhaled metabolites during and after the exacerbation, we will perform a paired-sample t-test to

evaluate differential concentrations of such metabolites. False discovery rate and q-values will be subsequently computed as defined by Storey.(60) To account for instrumental drift (e.g., detector sensitivity), the mass spectra are normalized using standard methods such as interquartile range, total ion current. Well-established data reduction techniques such as principal component analysis will be used for visualization purposes. Finally, high mass resolution/high mass accuracy data obtained will allow us to query online databases (e.g., human metabolome database) to provide tentative identification of the subset of most informative exhaled compounds. The preprocessing of the raw mass spectra and the statistical analysis will be implemented using MATLAB (MathWorks, Massachusetts, US).

For correlation analysis, the Pearson's linear correlation coefficient and 95% bootstrap confidence intervals will be applied. Continuous data will be summarized by means (SD) or medians (quartiles) as appropriate. A two-sided p value of <0.05 will be considered to be statistically significant for all tests.

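### Pearson's r with a bootstrap interval, the only method named for the secondary outcome, cannot handle multi-category agents or treatments and gives intervals that are too narrow at n=40

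*Combined protocol and SAP*

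**What the plan says.** Section 3.2.2 defines the secondary outcome as the correlation of breath metabolites with mMRC and CAT scores and with "inflammation markers (CRP and eosinophils, exhaled NO), causative agents (sputum microbiology and viral swabs) and treatment (inhalational drugs, steroids, antibiotics". Section 3.1.2 is wider: "molecular breath patterns will be assessed for correlation and association to clinical outcomes and treatment".

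Section 5.1 supplies one method for all of this: "For correlation analysis, the Pearson's linear correlation coefficient and 95% bootstrap confidence intervals will be applied". It does not name the type of bootstrap, say how agents or treatments are coded, or say which visit or change score enters each correlation. Its one allowance for skew concerns summaries only: "Continuous data will be summarized by means (SD) or medians (quartiles) as appropriate". Significance is judged at two-sided p<0.05.

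The variables are of different kinds. Section 4.5.8.1 says "The mMRC dyspnea score is a 5-point (0-4) scale based on the severity of dyspnea", and gives CAT a total out of 40. Agents are available at one visit only: "Sputum samples and viral smear is collected routinely during the clinical assessment during hospitalization (visit 1". The Appendix schedules CRP, eosinophils, FeNO and the questionnaires at both visits.

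No other method is tied to this outcome. In section 5.1 the paired t-test and q-values serve the comparison during versus after exacerbation, and principal components are for display. The statistics in the synopsis name no method for it. The machine learning in section 8.4 is unspecified and not linked to it. Section 5.2 calls the study exploratory, sets 40 complete pairs and states no power target.

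**The concern.** A single linear coefficient is asked to serve a sum score, a five-level score, three laboratory or breath markers, microbiology and virology results, and drug classes. Three things are at stake.

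- Where a factor has several unordered categories, the named method cannot be applied sensibly, so the real method would be chosen after the data are seen.
- Intervals that are too narrow would present unrelated metabolites as associated more often than the stated 95% implies. In an untargeted screen this feeds directly into the list of candidates.
- If markers and intensities are strongly right-skewed, a few large values can dominate r, and real associations may be missed.

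**Working it through.** **Inputs.** n=40 (5.2); two-sided 0.05 (5.1); mMRC in five levels and CAT out of 40 (4.5.8.1). The documents give no SDs, distributions, target r or power, so there is no plan figure to reproduce. Spread is therefore an assumption, shown mainly over log-SD 0.3 to 1.0.

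**1. What n=40 can show.** The Fisher-z interval is tanh(atanh r ± 1.96/√37), where 1.96/√37 = 0.322. For r=0.3, atanh r = 0.310, so the limits are tanh(−0.013) = −0.01 and tanh(0.632) = 0.56. The smallest r with 80% power in one test is tanh((1.96+0.842)/√37) = tanh(0.461) = 0.43.

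**2. Three unordered categories.** Assume categories A, B and C with 14, 13 and 13 patients, means 0, 1 and 0, and within-category SD 1. With p = 13/40 = 0.325, the variance between means is p(1−p) = 0.219, the total variance is 1.219 and the total SD is 1.104. The true strength is eta = √(0.219/1.219) = 0.42.

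- Numbered A=0, B=1, C=2: mean code 0.975, code SD 0.821, covariance 13/40 − 0.975×0.325 = 0.008. So r = 0.008/(0.821×1.104) = 0.01.
- Numbered A=0, B=2, C=1: same mean and SD, covariance 26/40 − 0.975×0.325 = 0.333. So r = 0.333/(0.821×1.104) = 0.37.

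Over all six numberings r runs from −0.37 to +0.37 for one and the same relation.

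**3. Two categories.** Here t = r√(n−2)/√(1−r²) is exactly the pooled two-sample t statistic. In a 20 versus 20 check both tests gave p=0.454. Pearson is valid in this case.

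**4. The interval.** The table shows how often a nominal 95% interval excludes a true zero (n=40, independent lognormal variables, 3,000 data sets, 1,000 resamples; Monte Carlo SE near 5% is √(0.05×0.95/3000) = 0.4 points).

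| Interval | log-SD 0.3 | 0.5 | 0.8 | 1.0 |
|---|---|---|---|---|
| Percentile, raw Pearson | 6.8% | 8.5% | 9.1% | 10.8% |
| Percentile, raw Pearson, separate run | 7.6% | 6.5% | 8.8% | 9.8% |

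Over the same range:

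- BCa for raw Pearson gave 6.5–8.2%.
- A percentile bootstrap for Pearson on logs gave 6.7–7.2%.
- A percentile bootstrap for Spearman gave 4.7–5.3% (3.6–5.0% in a run of 1,000 data sets).
- Fisher-z on logs gave 4.8–5.4%.
- The p-value test for r stayed at 4.6–5.1%.

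Most of the excess is present without skew: the percentile rate was 7.1% at log-SD 0.01. With mMRC as one variable the percentile rates were 6.8–7.7% for Pearson and 4.3–5.5% for Spearman. At latent r=0.4 between two lognormal variables, percentile coverage was 91–93% for raw Pearson and 95–96% for Spearman. For scale, among 1,000 unrelated pairs, 7–11% is 70 to 110 false exclusions instead of 50.

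**5. Power for markers under two models** (n=40, 10,000 runs).

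| Model | Method | log-SD 0.3 | 0.5 | 0.8 | 1.0 |
|---|---|---|---|---|---|
| Both lognormal, latent r=0.4 | raw Pearson | 71% | 65% | 56% | 48% |
| Both lognormal, latent r=−0.4 | raw Pearson | 71% | 64% | 42% | 25% |
| Both lognormal, either sign | Spearman | 68–69% | 68–69% | 68–69% | 68–69% |
| Metabolite linear in raw lognormal marker, r=0.4 | raw Pearson | 73% | 71% | 66% | 59% |
| Same | Spearman | 66% | 59% | 46% | 36% |

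Repeat runs of the log-SD 1.0 cells in the first two rows gave about 47% and 24%. In the last two rows Spearman loses 7, 12, 20 and 23 points.

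**6. mMRC by itself.** Five levels were cut from a latent normal (r=0.4) with a normal metabolite. With assumed shares of 2/5/13/35/45%, power is 63% for Pearson and 60% for Spearman. With 10/20/40/20/10% it is 69% and 65%.

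**The case against.** The strongest reply is that the power argument depends on the model chosen. If the metabolite rises linearly with the raw marker, Pearson is the better test even when the marker is heavily skewed, and the documents give neither the distributions nor the form of the relation. This stands, and it is why power is reported here as conditional.

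Steroids, antibiotics and positive or negative swabs can naturally be recorded as yes/no, where Pearson is sound. This also stands. It leaves the gap for pathogens or drug classes with three or more categories, and the plan does not say which coding it will use.

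The bootstrap type is unnamed, so the plan cannot be held to the percentile version. True, but BCa is also too narrow, and most of the excess appears with near-normal data. The p-value test holds its level, so formal significance is protected. The reported intervals are not, and interval and p-value can disagree.

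A reader might go further and infer that five ordered levels alone make Pearson unsuitable for mMRC. Step 6 shows no loss from ordinality itself; the reasons for Spearman there are the interval and protection against skewed intensities.

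A reader might also infer that the primary paired t-test is run on the wrong scale, since section 5.1 lists no log step. The documents do not support that, because "For data processing, we will follow the same procedure as described in our previous studies" refers to a procedure outside them. It is also a separate, primary-outcome question.

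**Conclusion.** The concern holds in three parts of unequal strength.

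- **Firm, no distributional assumption needed:** for three or more unordered categories Pearson's r is arbitrary, and the plan gives no other method.
- **Firm at n=40 for the cases simulated:** the bootstrap interval for Pearson's r excludes a true zero in about 7–11% of data sets (percentile) or 6.5–8% (BCa) instead of 5%. The excess is present with near-normal data and grows somewhat with skew. A Spearman percentile bootstrap holds about 5%.
- **Conditional:** raw Pearson loses about 20 points of power (r=0.4) to 45 points (r=−0.4) against Spearman at log-SD 1.0 if both variables are right-skewed and related multiplicatively. It gains about 23 points if the relation is linear in the raw marker. At log-SD 0.3 under the multiplicative model the two are within about 2 to 3 points.

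The point concerns the interpretability and interval coverage of an exploratory secondary outcome. It does not touch the sample size or the primary test, and since no power target is stated, none is missed. It should be corrected before the analysis, but does not threaten the study.

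**What to change.** Amend section 5.1 to name a method for each type of variable.

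1. mMRC: Spearman with a percentile bootstrap 95% interval.
2. CRP, eosinophils and exhaled NO: Spearman with a percentile bootstrap interval as the prespecified analysis, with raw or log-scale Pearson beside it as a sensitivity analysis. Reporting both covers the two models in step 5.
3. CAT: keep Pearson. Wherever Pearson is used on near-normal or logged data, take the interval from Fisher's z.
4. Causative agents (with visit 1 intensities) and treatments: yes/no group comparisons, or ANOVA or Kruskal-Wallis for three or more categories, with differences and 95% intervals. State the coding in advance.
5. For every other association, state whether visit 1, visit 2 or the change is used.

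The cost is a few lines of text and code, with no extra patients or data. The downside is power: Spearman gives up about 2 points at low skew, and 7 to 23 points in the table above (8 to 24 in another assessment) if the association is linear in a raw skewed marker. Results for mMRC and the markers would also be reported as rank correlations, which are less direct to read than a linear slope.

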Investigators from University Hospital Zurich	
[name]. med. [name], Pulmonary Division, University Hospital Zurich, [name], Switzerland. [contact]
 
[name], RPh, Pulmonary Division, University Hospital Zurich, [name], Switzerland. [contact]
 
[name], Pulmonary Division, University Hospital Zurich, [name], Switzerland. [contact]
 
[name], Pulmonary Division, University Hospital Zurich, [name], Switzerland. [contact]

Study Centre	Pulmonary Division, University Hospital Zurich, [name], Switzerland
Statistical Considerations	
To test the hypothesis if there is a significant difference in the values of exhaled metabolites during and after COPD exacerbation, we will perform a paired-sample t-test to evaluate differential concentrations of such metabolites. False discovery rate and q-values will be subsequently computed as defined by Storey.(7) Well-established data reduction techniques such as principal component analysis will be used for visualization purposes. Finally, high mass resolution/ high mass accuracy data obtained will allow us to query online databases (e.g., human metabolome database) to provide tentative identification of the subset of most informative exhaled compounds. The pre-processing of the raw mass spectra and the statistical analysis will be implemented using MATLAB (MathWorks, Massachusetts, US).

GCP Statement	
This study will be conducted in compliance with the protocol, the current version of the Declaration of Helsinki(8), the principles of Good Clinical Practice and as well all national legal and regulatory requirements in Switzerland.

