5.2 Sample Size calculation

As this is an exploratory study it is not possible to perform a conventional sample size calculation. Based on the results of our published previous study including a control group(18), a group size of 40 patients has been chosen for this longitudinal study. Overall recruitment of patients will last until the targeted sample size is reached and full data sets of 40 subjects are acquired (two visits with breath analysis).

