8.4 Details of the Secure Handling of Data connected to DBI

Data will be collected at University Hospital Zurich premises only by using Hardware and data acquisition tools (software), under the medical and administrative supervision and control of USZ. Data collection, data storage and data analytics will be described in more details in the following:

Medical records and de-identification of patients

All patients data will be de-identified by providing only a patient number with corresponding labels (gender, age, COPD stage/healthy,..) to DBI. This file is stored at DBI. DBI will not get any additional medical records other than these evaluated during the study visits.

Data collection and Data transfer

The unique patient identifier (number) will be used for the data collection as the only label received from USZ, added to the corresponding data acquired. The time series of data spectra will be locally encrypted on Hardware, transferred via internet to a Swiss-based, secure cloud storage, stored in encrypted state in the cloud, and transferred and finally decrypted at DBI. DBI will report the de-identified and clustered output data to USZ.

Data analytics at DBI

At DBI, data will be subdivided into temporal series of data and merged with the relevant labels (gender, age, GOLD status, ...) Based on the subject-matter expert input, all data will be analyzed regarding specific VOCs in a targeted way (using a data subset with filtered VOCs levels) or broadband in a untargeted way (using the full spectrum). Various Machine Learning (“ML”) and Artificial Intelligence (“AI”) algorithms will be tested.

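### Storey q-values are planned for the metabolite t-tests but given no decision role, while the only stated significance rule is raw p<0.05 for every test

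*Combined protocol and SAP*

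**What the plan says.** Section 5.1 tests the difference between the exacerbation visit and the 8-week visit with a paired t-test on exhaled metabolites. The next sentence reads "False discovery rate and q-values will be subsequently computed as defined by Storey", and the synopsis (Statistical Considerations) says the same. Neither place names a q cut-off or says what the q-values are used for.

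Section 5.1 closes with the only significance rule in the documents: "A two-sided p value of <0.05 will be considered to be statistically significant for all tests".

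The plan then looks for "tentative identification of the subset of most informative exhaled compounds", without saying whether p, q or something else picks that subset.

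For the secondary correlations, 5.1 says that Pearson's "linear correlation coefficient and 95% bootstrap confidence intervals will be applied". The q-value sentence follows the t-tests and is not linked to the correlations. Section 3.2.2 lists what the metabolites are to be correlated with: the mMRC and CAT symptom scores, then "inflammation markers (CRP and eosinophils, exhaled NO), causative agents (sputum microbiology and viral swabs) and treatment (inhalational drugs, steroids, antibiotics".

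On the status of the study, section 5.2 says "As this is an exploratory study it is not possible to perform a conventional sample size calculation".

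**The concern.** The primary outcome (3.2.1) is the change in exhaled metabolites as a group, with no metabolite singled out. The primary result is therefore a list of features declared changed, and its quality depends on the rule that admits a feature to it.

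Two rules can be read from 5.1. Computing q-values suggests that q should decide. The closing sentence says that raw p<0.05 decides, with no exception for the metabolite tests. Depending on how many features truly change, the two rules can give lists that differ several-fold in length and roughly ten-fold in false share. The list also feeds compound identification and any pathway interpretation. Section 2.5 itself notes that reported breath biomarkers have not overlapped between studies and that statistical methods are not standardised, so a list of unknown false share would add to that problem.

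**Working it through.** **Figure to reproduce.** There is none. The 40 patients in 5.2 were chosen by reference to an earlier study, with no power, effect size, SD or error rate.

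**Inputs from the documents.** 40 complete pairs (5.2); two-sided 0.05 and a paired t-test (5.1).

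**Inputs assumed.** Number of features m = 1000; standardised paired change d_z = 0.5 for features that truly change; null share p0 (the fraction that do not change) from 50% to 95%; independent features. Correlation, m and d_z are varied below.

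**Step 1: power per true feature.** From the noncentral t with 39 degrees of freedom and noncentrality d_z × √40, power at p<0.05 is 0.457, 0.694, 0.869 and 0.959 for d_z = 0.3, 0.4, 0.5 and 0.6.

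**Step 2: false share of a p<0.05 list.** False share = p0 × 0.05 / [p0 × 0.05 + (1 − p0) × power]. At d_z = 0.5:

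- p0 = 0.50: 0.025 / (0.025 + 0.4345) = 5%
- p0 = 0.80: 0.040 / (0.040 + 0.1738) = 19%
- p0 = 0.90: 0.045 / (0.045 + 0.0869) = 34%
- p0 = 0.95: 0.0475 / (0.0475 + 0.04345) = 52%

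The raw p cut-off that would hold the false share at 5% is about 0.045, 0.0086, 0.0029 and 0.0010 respectively. So p<0.05 is close to the right cut-off only when about half of all features change.

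**Step 3: simulation with Storey q (lambda = 0.5).** Mean number declared / mean number false, m = 1000, d_z = 0.5:

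| Null share | p<0.05 | q<0.05 |
|---|---|---|
| 50% | 459.6 / 25.3 | 451.4 / 22.8 |
| 80% | 214.1 / 40.1 | 137.9 / 6.9 |
| 90% | 131.8 / 44.9 | 53.5 / 2.8 |
| 95% | 91.0 / 47.4 | 19.8 / 1.1 |

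The false share under q<0.05 is 22.8/451.4 = 5.1%, 6.9/137.9 = 5.0%, 2.8/53.5 = 5.2% and 1.1/19.8 = 5.6%.

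**Step 4: no true change.** p<0.05 declares 1000 × 0.05 = 50 features on average; q<0.05 declares about 0.06.

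**Step 5: sensitivity.**

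- Correlated features (r = 0.5 in blocks of 20), 95% null: 91.2 / 47.8 under p<0.05 and 19.4 / 1.1 under q<0.05, so the means hardly move. With no true change, the p<0.05 count still averages about 50 but varies more from study to study (central 95% interval 28 to 78).
- 500 features, 95% null: 45.6 / 23.8 and 10.2 / 0.6. The counts halve and the shares stay.
- Effect size, d_z from 0.6 down to 0.3: the false share under p<0.05 is 17% to 30% at 80% null, 32% to 50% at 90%, and 50% to 68% at 95%.

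**Step 6: correlations.** Section 3.2.2 names ten items. With 1000 features that is 10,000 pairs. If none were truly related, about 10,000 × 0.05 = 500 nominal 95% intervals would exclude zero. This matters only if exclusion of zero is treated as a finding, and the plan does not say whether it is.

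**The case against.** The strongest reply is that multiplicity has been dealt with. Storey q-values stand directly after the t-test in both the synopsis and 5.1, and the natural reason to compute them is to use them. In a study that calls itself exploratory, a missing clause is then a matter of clarification. Much of this stands. A reader might infer that the plan has no multiplicity control for its primary comparison, and the documents do not support that. They plan the right quantity but give it no decision role, and the closing rule, read literally, overrides it. Exploratory status removes any need for familywise control. It does not remove the value of a list with a known false share, and the plan still tests a stated hypothesis and declares significance.

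A reader might also infer that the rule is left open until the data are seen. That goes too far: the literal text fixes p<0.05 in advance. The defect is a conflict between that rule and the planned q-values.

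A third reply is that change may be widespread. Visit 1 takes place during a hospitalised exacerbation, within 48 hours of starting antibiotics or systemic steroids, so many features could shift. This stands as a possibility: at 50% null the two rules give almost the same list. The documents do not say where in the range the study will fall.

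Two further complaints are tempting and weak. The number of features is not stated, but in untargeted spectra it is known only after processing. Section 8.4 allows a filtered subset or analysis "broadband in a untargeted way (using the full spectrum", but that describes the partner's machine-learning work and does not show that the t-test family is undefined. The reference in 5.1 to earlier studies covers data processing and does not supply a decision rule.

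Finally, r with an interval is estimation. Requiring multiplicity adjustment of every correlation would be a preference, so that part is only a note.

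**Conclusion.** The point holds as a conflict between the stated rule and the planned q-values, and it should be settled before analysis. Applied as written, p<0.05 per feature gives a primary list whose false share is about 5% if half the features are unchanged and about 52% if 95% are. A q<0.05 rule holds it at about 5% across that range. If nothing changes, the written rule declares about 50 of 1000 features.

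These sizes rest on assumed feature counts, null shares and effect sizes, none of which the documents give. They show scale and do not predict this study's result. The direction does not depend on the exact feature count and, in the case examined, was not altered by correlation between features. The gap between the rules nearly vanishes at the favourable end.

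**What to change.** Replace the last sentence of 5.1 with:

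> A metabolite feature is declared changed between visits only if its Storey q is below 0.05; all features tested are reported ranked by q, with their number. Raw p<0.05 is not used to declare metabolite features.

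Make the synopsis agree.

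Add a short note on the correlations: report r with 95% bootstrap intervals for all features examined, label them descriptive, and make no significance claim. Do not restrict them to features that pass q. When few pass, that would nearly empty the secondary objective, and it would drop metabolites that track CRP or eosinophils without changing between visits. If any correlation is to be called significant, control the false discovery rate jointly over all metabolite-by-variable pairs tested.

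The cost in work is a few sentences and no new data. The real cost is true features not declared. With 1000 features of which 50 truly change (95% null), mean true declarations at d_z = 0.5 fall from about 43 under p<0.05 to about 19 under q<0.05. At d_z = 0.3 they fall from about 23 to about 1, although 68% of that p<0.05 list would be false. The full ranked list reduces the loss, because features just short of the cut-off remain visible for follow-up.
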